4.3.2.3. Immunogenicity analysis: CMI response

The analysis will be based on the CMI subset of the PPS. If, in any group, the percentage of vaccinated participants with serological results excluded from the CMI subset of the PPS is more than 5%, a second analysis based on the CMI subset of the ES will be performed to complement the PPS analysis.

At each time point blood samples are collected, the following parameters will be summarized by group using descriptive statistics (N, geometric mean, min, Q1, median, Q3, max) in the CMI subset:

- Frequency of RSVPreF3-specific CD4+ and/or CD8+ T cells expressing at least 2 activation markers including at least one cytokine among CD40L, 41BB, IL-2, TNF- α , IFN- γ , IL-13, IL-17, measured by intracellular cytokine staining (ICS) using Peripheral Blood Mononuclear Cells (PBMCs).
- The kinetics of the frequency of RSVPreF3-specific CD4+ T cells expressing at least 2 activation markers including at least one cytokine among CD40L, 41BB, IL-2, TNF- α , IFN- γ , IL-13, IL-17, measured by ICS, will be plotted as a function of time for participants with results available at all timepoints.
- Fold increase of the frequency of RSVPreF3-specific CD4+ T cells expressing at least 2 activation markers including at least one cytokine among CD40L, 41BB, IL-2, TNF- α , IFN- γ , IL-13, IL-17, measured by ICS at the post-vaccination time point over pre-vaccination (Visit 1, Day 1). The percentage of subjects with at least a 4-fold increase, post-vaccination as compared to pre-vaccination will be tabulated by timepoint.
- The frequency of RSVPreF3 specific-CD4+ T cells expressing at least 2 activation markers including at least one cytokine among CD40L, 41BB, IL-2, TNF- α , IFN- γ , IL-13, IL-17, measured by ICS, will be displayed graphically using boxplots (min, Q1, median, Q3, max)

The above mentioned descriptive within group immunogenicity analysis will also be generated by age at vaccination (50-59 YOA, 60-69 YOA, 70-79 YOA and ≥ 80 YOA years) at the exception of the graphical displays

4.3.3. Additional considerations

4.3.3.1. Mixed-effects model

For the GMTs calculation based on the mixed effects model mentioned in Section 4.3.2.2, repeated measures analysis of covariance (ANCOVA) model will be fitted including study group (OA-RSV, Adults-AIR-RSV, Adults-AIR-Placebo, Adults-HA-RSV, Adults-HA-Placebo) and post-vaccination visit (Day 31, Months 6, 12), as fixed effects, pre-vaccination log10-transformed titers as a covariate and the response variable is the post-vaccination log10-transformed titers. The PROC MIXED procedure in SAS® will be used to carry out the ANCOVA.

The following SAS codes will be used:

```
PROC MIXED DATA=SERO method=reml empirical;
  CLASS subjID group visit ;
  MODEL post-vac=pre-vacc group visit visit*group/ noint s cl;
  REPEATED visit/ type=un subject=subjID;
  LSMEANS visit*group/ E cl;
  ODS OUTPUT LSMEANS=LS;
  RUN;
```

The above SAS codes may be adapted in case of convergence issues.

4.3.3.2. Cell-mediated immune response

The RSVPreF3-specific CD4+/ CD8+ T cell frequencies will be obtained by subtracting the background value to the antigen-induced value, and by setting to 1 all values less than or equal to zero for geometric mean calculation and graphical representation. Frequencies will be expressed as the number of cells per million of CD4+/ CD8+ T cells.

More specifically, the frequencies of RSVPreF3-specific CD4+/ CD8+ T cells expressing at least 2 activation markers including at least one cytokine [$Freq^{2+}$] will be computed as follows:

$$Freq_{Background}^{2+} = \frac{n_{Background}^{2+}}{N_{Background}^{CD4}} \quad \text{and} \quad Freq_{Induction}^{2+} = \frac{n_{Induction}^{2+}}{N_{Induction}^{CD4}},$$

and

$$Freq_{Specific}^{2+} = Freq_{Induction}^{2+} - Freq_{Background}^{2+}$$

where

$n_{Background}^{2+}$ = number of CD4+ T cells expressing at least 2 activation markers including at least one cytokine after stimulation with medium only (background)

$n_{Induction}^{2+}$ = number of CD4+ T cells expressing at least 2 activation markers including at least one cytokine after stimulation with a pool of peptides covering RSVPreF3 (induction)

$N_{Back/Ind}^{CD4}$ = Total number of CD4+ T cells involved in the assay (background or induction)

[figure not shown]
For the computation of the fold increase (post- over pre-vaccination) of the frequency of RSVPreF3-specific CD4+ T-cells identified as expressing at least 2 activation markers including at least one cytokine among CD40L, 41BB, IL-2, TNF- α , IFN- γ , IL-13, IL-17, the results below the lower limit of quantification (LLOQ) of the assay will be replaced by the value of the LLOQ.

4.3.3.3. Atrial Fibrillation (AF) AESIs

Potential AF AESIs will be identified through the MedDRA preferred term of interest atrial fibrillation (10003658). Sites will be prompted via query to complete any necessary additional information for these AESIs in the eCRF. Additional analysis might be performed on those additional data collected for AF AESIs.

AF AESIs will be described in a tabular summary including the characteristics of the AE (seriousness, causality, maximum intensity), time to onset and outcome.

[figure not shown]
CCI

CONFIDENTIAL

219238

[figure not shown]
CCI

CONFIDENTIAL

219238

CCI

CCI

4.5. Other Safety Analyses

Not Applicable.

4.6. Other Analyses

Not Applicable.

4.7. Interim Analyses

All analyses will be conducted on final data, as clean as possible.

4.7.1. Sequence of analyses

The analyses will be performed stepwise:

- **Day 31 (PCA):** A first analysis will be performed on all immunogenicity, reactogenicity and safety data available and as clean as possible, when data for at least primary and secondary endpoints up to Visit 2 (Day 31) are available for all participants. This analysis will be considered as final for those endpoints*.
- **Month 6:** A second analysis will be performed on all immunogenicity and safety data available and as clean as possible, when data for at least secondary endpoints up to Visit 3 (Month 6) are available for all participants. This analysis will be considered as final for those endpoints*.
- An **end of study** analysis will be performed when all data for at least secondary endpoints up to study conclusion (Visit 4, Month 12) will be available for all participants.

- If the data for tertiary endpoints become available at a later stage, (an) additional analysis/analyses will be performed.
 - * Each analysis can be considered as final, as it is based on data that is as clean as possible. However, the consecutive analysis of the same time point might slightly differ at the next analysis e.g., when Month 6 data are re-analyzed at the time of Month 12 analysis. If major changes are identified, they will be described in the clinical study report.

4.7.2. Statistical considerations for interim analysis

No statistical adjustment for interim analysis is required.

4.8. Changes to Protocol Defined Analyses

There were no changes or deviations to the originally planned statistical analysis specified in the protocol (Dated: 26-JUL-2022).

5. SAMPLE SIZE DETERMINATION

The target sample size for the study is approximately 1520 participants: 380 participants each in the Adults-HA-RSV Group and Adults-AIR-RSV Group, 190 participants each in the Adults-HA-Placebo Group and Adults-AIR-Placebo Group and 380 participants in the OA-RSV Group.

The sample size in the groups receiving the investigational vaccine is driven by the statistical power to prove the primary NI objectives.

Assuming 342 evaluable participants in each group receiving the investigational vaccine, the power to demonstrate the primary NI objectives following the graphical testing procedure in Section 2.1 is presented in [Table 4](#). Power was estimated by 10 000 simulations, using SAS 9.4:

- Individual RSV-A and RSV-B neutralizing titers at baseline and at 1-month post-study intervention administration were modeled by a multivariate log-normal distribution, means and variance-covariance matrix based on historical data from other RSV OA vaccine clinical trials. The Adults-AIR-RSV Group was assumed to have the same multivariate log-normal distribution of the OA-RSV Group (i.e., same means and variance-covariance matrix), while the Adults-HA-RSV Group was assumed to have a 1.25-fold higher mean at 1-month post-study intervention administration for both neutralizing antibodies.
- Raw p-values were obtained from shifted 1-sided t-tests (for group GMT ratios) and using the method of Miettinen and Nurminen (for group SRR difference). The p-value associated to each NI objective is the maximum between the p-values from the GMT ratio and from the SRR difference (co-primary endpoints).

- P-values associated to each NI objective were compared with the corresponding alpha, as propagated by the graphical testing procedure, to identify which NI objectives were successfully demonstrated at each simulation.

Table 4 Power of primary NI objectives

Objective	Power
NI in the Adults-HA-RSV Group for the RSV-A strain	>99%
NI in the Adults-HA-RSV Group for the RSV-B strain	>99%
NI in the Adults-AIR-RSV Group for the RSV-A strain	93.6%
NI in the Adults-AIR-RSV Group for the RSV-B strain	82.8%
All	82.7%

All=power to demonstrate all primary NI objectives simultaneously; AIR=At increased risk; HA=Healthy adults; NI=Non-inferiority; RSV=Respiratory syncytial virus.

A 10% attrition rate is accounted from enrolled to evaluable participants. Participants who withdraw from the study will not be replaced.

6. SUPPORTING DOCUMENTATION

6.1. Appendix 1 Study Population Analyses

6.1.1. Participant Disposition

A summary of the number and percentage of participants who completed the study as well as those who prematurely withdrew from the study will be provided. Reasons for study withdrawal will be summarized. This analysis will be based on the Screened set, Enrolled set, ES.

6.1.2. Demographic and Baseline Characteristics

Demographic and baseline characteristics (age at vaccination in years, sex, race, ethnicity, country, vital signs, Body Mass Index (BMI) and smoking status) will be summarized by group using descriptive statistics, as described in Section 4.1.1. This analysis will be based on all analysis sets.

The following age categories will be considered in the analysis: 50-59 YOA, 60-69 YOA, 70-79 YOA and ≥ 80 YOA. In addition, for web posting purposes: 18-64 YOA, 65-84 YOA and ≥ 85 YOA.

CCI

6.1.3. Protocol Deviations

Protocol deviations will be tracked by the study team throughout the conduct of the study. These protocol deviations will be reviewed to identify those considered as important as follows:

- Data will be reviewed prior to unblinding (at the Day 31 Analysis) and freezing the database to ensure all important deviations (where possible without knowing the study intervention details) are captured and categorised in the protocol deviations dataset and all deviations leading to exclusions from analysis sets are captured.
- This dataset will be the basis for the summaries of important protocol deviations.

A summary of important protocol deviations leading to exclusions from any analysis set will be provided by group, based on the Screened Set.

The number of participants screened for the study as well as the number of participants excluded from the Enrolled set, ES and the PPS analyses will be tabulated. These will be based on the Screened set, Enrolled Set and the ES, respectively.

6.1.4. Participant exposure

The number and percentage of participants who received the study intervention will be tabulated by group for the ES.

6.1.5. Concomitant Medications

Concomitant medications will be coded using the WHO Drug dictionary.

The number and percentage of participants using concomitant medication (any medication, any antipyretic and any antipyretic taken prophylactically) during the 4-day and the 30-day follow-up period after vaccination will be tabulated with exact 95% CI per study group.

6.1.6. Concomitant Vaccinations

The number and percentage of participants and doses with concomitant vaccination during the 30-day follow-up period (i.e., on the day of vaccination and 29 subsequent days) will be tabulated with exact 95% CI per study group.

6.1.7. Additional Analyses due to the COVID-19 Pandemic

Would COVID-19 still be classified as pandemic in one of the study countries, the following analyses will be performed:

A standardized MedDRA Query (SMQ) will be used to identify all COVID-19 AEs.

The overall incidence of COVID-19 AEs (during the 30-day follow-up period), COVID-19 SAEs and COVID-19 AEs leading to study withdrawal (from vaccination up to study end) will be summarized. The incidence of these events will be obtained from standard AE and SAE summaries (i.e., by SOC and PT).

COVID-19 assessments (confirmed, probable and suspected diagnosis) for participants with COVID-19 AEs will be summarized.

The number and percentage of participants with previous or concomitant COVID-19 vaccination, before and during the study (during the 30-day follow-up period after vaccination), will be tabulated with exact 95% CI.

6.2. Appendix 2 Data Derivations Rule

6.2.1. Attributing events to vaccine doses

If an event starts on the same day as a study dose, the relative dose will be derived from the additional information provided in the eCRF using the contents of the flag indicating if the event occurred before or after study dose. If ‘after study dose’ is selected, the relative dose for the event will be the one administered on the start day of the event. If ‘before study dose’ is selected, the event will not be attributed to the study vaccination.

6.2.2. Handling of missing data

6.2.2.1. Dates

When partially completed dates (i.e., dates missing a day and/or month) are used in calculations, the following standard rules will be applied:

- A missing day will be replaced by 15
- A missing day and month will be replaced by June 30th.

The following exceptions apply:

- Adverse events start dates with missing day:
 - If the month is not the same as the vaccine dose, then the imputed start date will be the 1st of the month.
 - If the event starts in the same month as the vaccine dose, the flag indicating if the event occurred before or after vaccination (AE.AESTRTPT) will be used to complete the date. If ‘after vaccination’ is selected, the imputed start date will match the vaccine dose given during that month. If ‘before vaccination’ is selected, the imputed date will be one day before the vaccine dose given during that month.
- Adverse events start dates with missing day and month:
 - If the year is not the same as the vaccine dose, then the imputed start date will be the 1st of January.
 - If the event starts in the same year as the vaccine dose, the flag indicating if the event occurred before or after vaccination (AE.AESTRTPT) will be used to complete the date. If ‘after vaccination’ is selected, the imputed start date will match the vaccine dose given during that year. If ‘before vaccination’ is selected, the imputed date will be one day before the vaccine dose given during that year.
- Adverse event end dates with missing day: the imputed end date will be the last day of the month or the study conclusion date whichever comes first.

- Adverse event end dates with missing day and month: the imputed end date will be the last day of the year (31st of December) or the study conclusion date whichever comes first.
- All incomplete concomitant medication/vaccination start/end dates will follow the rules above.

6.2.2.2. Laboratory data

Any missing or non-evaluable immunogenicity measurement will not be replaced. The descriptive analysis performed for each assay at each timepoint will exclude participants with a missing or non-evaluable measurement. This is applicable to the standard way of computing geometric mean titers/concentrations (GMTs/GMCs).

Computation of GMTs/GMCs from the mixed effects model inherently accounts for the missingness, under the assumption that the missing data are missing at random (MAR). Subject having missing pre-vaccination titer will be excluded from ANCOVA and mixed effects models (refer Section 4.3.3.1)

6.2.2.3. Daily recording of solicited events

For studies using paper diaries which have questions in the CRF indicating the presence or absence of solicited events, the following rules are applicable:

- Denominators for the summary of administration site (or systemic) solicited events will be calculated using the number of participants who respond “Yes” or “No” to the question concerning the occurrence of administration site (or systemic) events.
- When a specific solicited event is marked as having not occurred following a specific study dose (i.e. SDTM CE.CEOCCUR=N for the specified post-dose period for the event in question), all daily measurements will be imputed as Grade 0.
- When a specific solicited event is marked as having occurred following a specific study dose (i.e. SDTM CE.CEOCCUR=Y for the specified post-dose period for the event in question), any missing daily recordings will be given imputed values to allow them to contribute to the ‘Any’ rows but not to specific grade rows of the solicited event summary tables.

The following table shows how participants contribute to each category for a specific solicited event over the Day X to Day Y post-dose period:

Solicited event category	Participants included in the calculation of the numerator
Any	All participants with at least one occurrence of the adverse event at grade 1, grade 2, or grade 3 between Day X and Day Y or with the adverse event marked as present and at least one missing daily recording between Day X and Day Y
At least grade 1	All participants with at least one occurrence of the adverse event at grade 1, grade 2, or grade 3 between Day X and Day Y
At least grade 2	All participants with at least one occurrence of the adverse event at grade 2 or grade 3 between Day X and Day Y
At least grade 3	All participants with at least one occurrence of the adverse event at grade 3 between Day X and Day Y

6.2.2.4. Unsolicited adverse events

Unsolicited adverse event summaries are including serious adverse events unless specified otherwise.

As per CDISC Vaccines Therapeutic Area guide, the solicited events which continue beyond the observation period are stored in the Adverse Events (AE) domain, but they do not contribute to the summaries of unsolicited adverse events.

Missing severity, relationship with study vaccine, and outcome of unsolicited adverse events will not be replaced and will appear as 'UNKNOWN' when displayed in a statistical output.

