
 
To demonstrate the NI** of the humoral immune response in participants 50-59 YOA at increased risk of RSV-LRTD compared to OA (≥60 YOA) for the RSV-B strain after RSVPreF3 OA investigational vaccine administration.
 
	
 
RSV-B neutralization titers expressed as group GMT ratio (OA-RSV/Adults-AIR-RSV), 1 month after the RSVPreF3 OA investigational vaccine administration***.
 
RSV-B neutralization-titers expressed as group SRR difference (OA-RSV - Adults-AIR-RSV), 1 month after the RSVPreF3 OA investigational vaccine administration compared to baseline***.
 
			
Secondar	y - Safety			
To evaluate the safety and reactogenicity after the RSVPreF3 OA investigational vaccine administration.	
 
Percentage of participants reporting each solicited administration site event with onset within 4 days after study intervention administration (i.e., the day of study intervention administration and 3 subsequent days).
 
Percentage of participants reporting each solicited systemic event with onset within 4 days after study intervention administration (i.e., the day of study intervention administration and 3 subsequent days).
 
Percentage of participants reporting unsolicited AEs within 30 days after study intervention administration (i.e., the day of study intervention administration and 29 subsequent days).
 
Percentage of participants reporting any SAEs and pIMDs after study intervention administration (Day 1) up to Month 6.
 
Percentage of participants reporting SAEs and pIMDs related to study intervention administration after study intervention administration (Day 1) up to study end (Month 12).
 
Percentage of participants reporting any fatal SAEs after study intervention administration (Day 1) up to study end (Month 12).
 
			
Secondary - In	nmunogenicity			
To evaluate the humoral immune response to the RSVPreF3 OA investigational vaccine until 12 months post-study intervention administration.	RSV-A and RSV-B neutralization-titers expressed as GMT, at pre-study intervention administration, 1 month, 6 months and at 12 months after study intervention administration.			

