#### 10.3.4. Unsolicited AEs

An unsolicited AE is an AE that was either not included in the list of solicited events or could be included in the list of solicited events but with an onset outside the specified period of follow-up for solicited events. Unsolicited AEs must have been communicated by a participant who has signed the informed consent. Unsolicited AEs include both serious and non-serious AEs.

Potential unsolicited AEs may be medically attended (i.e., symptoms or illnesses requiring a hospitalization, or an emergency room visit, or visit to/by a health care provider). The participants will be instructed to contact the site as soon as possible to report medically attended event(s), as well as any events that, though not medically attended, are of participant concern. Detailed information about reported unsolicited AEs will be collected by qualified site personnel and documented in the participant's records.

Unsolicited AEs that are not medically attended or perceived as a concern by the participant will be collected during an interview with the participants and by review of available medical records at the next visit.

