
 To demonstrate the NI of the humoral immune response in participants 50-59 YOA at increased risk of RSV-LRTD compared to OA (≥ 60 YOA) for the RSV-B strain after RSVPreF3 OA investigational vaccine administration. 	
 RSV-B neutralization titers expressed as group GMT ratio (OA-RSV/Adults-AIR-RSV), 1 month after the RSVPreF3 OA investigational vaccine administration. RSV-B neutralization titers expressed as group SRR difference (OA-RSV - Adults-AIR-RSV), 1 month after the RSVPreF3 OA investigational vaccine administration compared to baseline.
Secondary - Safety	

 To evaluate the safety and reactogenicity after the RSVPreF3 OA investigational vaccine administration. 	
 Percentage of participants reporting each solicited administration site event with onset within 4 days after study intervention administration (i.e., the day of study intervention administration and 3 subsequent days). Percentage of participants reporting each solicited systemic event with onset within 4 days after study intervention administration (i.e., the day of study intervention administration and 3 subsequent days).

[figure not shown]
Objectives	Endpoints and estimands
	
 Percentage of participants reporting unsolicited AEs within 30 days after study intervention administration (i.e., the day of study intervention administration and 29 subsequent days). Percentage of participants reporting any SAEs and pIMDs after study intervention administration (Day 1) up to Month 6. Percentage of participants reporting SAEs and pIMDs related to study intervention administration after study intervention administration (Day 1) up to study end (Month 12). Percentage of participants reporting any fatal SAEs after study intervention administration (Day 1) up to study end (Month 12).
Secondary - Immunogenicity	

 To evaluate the humoral immune response to the RSVPreF3 OA investigational vaccine until 12 months post-study intervention administration. 	
 RSV-A and RSV-B neutralization titers expressed as GMT, at pre-study intervention administration, 1 month, 6 months and at 12 months after study intervention administration.

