4.3.2. Main analytical approach

4.3.2.1. Safety analysis

The safety analysis will be performed per study group, on the ES, as follows:

- The number and percentage of participants with at least one administration site event (solicited and unsolicited), with at least one systemic event (solicited and unsolicited) and with any AE (solicited and unsolicited) during the 4-day or 30-day follow-up period after vaccination will be tabulated with exact 95% CI. The same computations will be done for Grade 3 AEs, for Grade 3 non-serious AEs and for AEs resulting in a medically attended visit.

Those analyses will present all solicited and unsolicited AEs, including SAEs (unless otherwise specified).

- The number and percentage of participants with at least one administration site event (solicited only), with at least one systemic event (solicited only) and with any solicited event during the 4-day follow-up period after vaccination will be tabulated with exact 95% CI. The same computations will be done for Grade 3 AEs and for AEs resulting in a medically attended visit.
- Compliance in completing solicited events information will be tabulated.
- The number and percentage of participants reporting each individual solicited administration site or systemic event (any grade, Grade 3 and resulting in medically attended visit) during the 4-day follow-up period after vaccination will be tabulated with exact 95% CI.
- For fever, the number and percentage of participants reporting fever by half degree ($^{\circ}\text{C}$) cumulative increments during the 4-day follow-up period after vaccination will be tabulated.

- The percentage of participants with each solicited administration site event and solicited systemic event (any grade and Grade 3) during the 4-day follow-up period after vaccination will be represented graphically.
- The duration in days of each individual solicited events will be tabulated using descriptive statistics (mean, min, Q1, median, Q3, maximum).
- The number of days with Grade 3 solicited events will be tabulated for each individual solicited event using descriptive statistics (mean, min, Q1, median, Q3, maximum).

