6.2.3.9. Duration of events

The duration of an event with a start and end date will be the difference between the start and end date plus one day, i.e., an event that starts on 03MAR2018 and ends on 12MAR2018 has a duration of 10 days.

For solicited administration site and systemic events:

- The duration of a solicited AE with at least one day Grade > 0 is defined as End date(CEENDY) – Start date(CESTDY) + 1, with Start date defined as the first day with the symptom and End date defined as the last day with the symptom in or beyond the solicited period.
- A missing start date will be imputed with the vaccination date.
- For paper diaries, if an ongoing symptom has a missing end date, the end date will be considered equal to vaccination date + 29 days. Partial end dates will be imputed according to section 6.2.2.1.
- The number of days with grade 3 solicited symptom will be defined considering each day with a known grading=3 (for paper CRF, if the max intensity during the ongoing period is 3, each day of the ongoing period will be counted as grade 3).

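### A non-serious solicited reaction that first reaches Grade 3 after Day 4 enters neither event-level Grade 3 incidence table, although the Grade 3-days table counts it

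*SAP*

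**What the plan says.** **Endpoint.** Both documents define the reactogenicity endpoints by onset and give no grade: "Percentage of participants reporting each solicited systemic event with onset within 4 days after study intervention administration" (Protocol Section 3, Table 3), with the parallel wording for administration site events in SAP 1.1.

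**Solicited Grade 3 incidence.** SAP 4.3.2.1 plans a table for each individual solicited event: "any grade, Grade 3 and resulting in medically attended visit) during the 4-day follow-up period after vaccination will be tabulated". The numerator rule for the Grade 3 category in SAP 6.2.2.3 is "All participants with at least one occurrence of the adverse event at grade 3 between Day X and Day Y". For this table, Day X to Day Y is Day 1 to Day 4.

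**Unsolicited Grade 3 incidence.** Protocol 10.3.4 allows a listed symptom to be unsolicited if it "could be included in the list of solicited events but with an onset outside the specified period of follow-up for solicited events". For the unsolicited tables, SAP 6.2.2.4 adds that "solicited events which continue beyond the observation period are stored in the Adverse Events (AE) domain, but they do not contribute to the summaries".

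**Grade 3 days.** SAP 4.3.2.1 also tabulates the number of Grade 3 days for each solicited event, with no 4-day limit stated. Under SAP 6.2.3.9, "if the max intensity during the ongoing period is 3, each day of the ongoing period will be counted as grade 3". The same section lets the end date fall after the solicited period, and sets a missing end date of an ongoing symptom in a paper diary to 29 days after vaccination.

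**Combined table.** The first bullet of SAP 4.3.2.1 plans tables of solicited and unsolicited events together over 4 or 30 days, repeated for Grade 3.

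**The concern.** Each rule is sensible by itself, but together they leave a gap. The solicited table takes severity from Days 1-4 only. The unsolicited table refuses the event because its onset was inside the window. A reaction that begins mildly and becomes severe on Day 5 or later therefore has no event-level table in which it is Grade 3. The SAP still treats its later severity as known, because it uses that severity to count Grade 3 days.

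At stake is the description of severe reactogenicity. Protocol 4.3 states that the vaccine has not been given in its present form at 50-59 years, and reactogenicity is a secondary safety objective. A reader who compares the two outputs could find a participant with several Grade 3 days for an event and no Grade 3 in that event's incidence row, with nothing in the SAP to explain it.

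**Working it through.** The documents give no figure to reproduce. The check applies the counting rules to hypothetical diary records.

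**Day-count convention.** The example in SAP 6.2.3.9 runs from 3 to 12 March: 12 - 3 + 1 = 10 days, as the SAP states. SAP 6.2.3.8 makes the vaccination day Day 1, so 29 days after vaccination is Day 30.

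**Rules applied**
- Solicited Grade 3: yes if any daily grade on Days 1-4 is 3 (4.3.2.1, 6.2.2.3).
- Unsolicited Grade 3: possible only if onset is after Day 4 (Protocol 10.3.4, SAP 6.2.2.4).
- Grade 3 days: Grade 3 days within Days 1-4, plus (end day - 4) if the ongoing-period maximum is 3 (6.2.3.9).
- Duration: end day - onset day + 1 (6.2.3.9).

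**Results**

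| Record | Solicited Grade 3 | Unsolicited Grade 3 | Grade 3 days | Duration (days) |
|---|---|---|---|---|
| A. Onset Day 2; grades 0, 1, 1, 2 on Days 1-4; ongoing to Day 8, maximum 3 | No | No | 8 - 4 = 4 | 8 - 2 + 1 = 7 |
| B. As A, end date missing (set to Day 30) | No | No | 30 - 4 = 26 | 30 - 2 + 1 = 29 |
| C. Onset Day 2; grades 0, 1, 3, 1; ends Day 4 | Yes | No | 1 | 4 - 2 + 1 = 3 |
| D. Same symptom, onset Day 5 at Grade 3, ends Day 8 | No | Yes | Not a solicited event | 8 - 5 + 1 = 4 |

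C and D are controls: each is counted once, in the table where it belongs. Only the pattern in A and B (onset in Days 1-4, first Grade 3 after Day 4) falls between the tables. A and B are still counted in the any-grade solicited row.

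**Other outputs.** The detailed listing in SAP 4.3.2.1 covers SAEs and AESIs only. The web-posting table is by system organ class and preferred term, with no grade stated. A serious event would appear in the SAE tables, so the gap concerns non-serious reactions.

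**Size.** If all planned participants answer the solicited-event question, one participant adds 100/380 = 0.26 percentage points in a vaccine group and 100/190 = 0.53 in a placebo group. The documents give no rates for the pattern in A. As a pure assumption, suppose 5-15% of a vaccine group have a solicited event ongoing after Day 4, and 2-10% of those first reach Grade 3 then:
- low: 380 x 0.05 x 0.02 = 0.4 participants (0.1 percentage points);
- high: 380 x 0.15 x 0.10 = 5.7 participants (1.5 percentage points).

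The low end may mean nobody. The high end multiplies two assumed maxima.

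**The case against.** The strongest reply is that these outputs measure different things and each is right as labelled. The incidence table says that it covers 4 days; the Grade 3-days table describes the whole event. A windowed incidence and a whole-event duration need not share a numerator. A fixed 4-day window graded daily is a defensible main figure, and is cleaner than one that adds a single maximum from a period of variable length, sometimes with an imputed end date. This stands, and it is why the main numerator should stay.

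Three further points also stand. First, a reader might infer that the protocol endpoint is breached. It is not: the endpoint is onset within 4 days with no grade, and the affected participant is counted there. Second, a reader might infer that SAP 6.2.2.4 is wrong. It is not: it follows Protocol 10.3.4, avoids double counting, and bars the event only from the unsolicited summaries. Third, the late severity is not wholly hidden. It shows in the Grade 3-days table, and the combined 30-day Grade 3 table may include it.

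What remains is narrower. The SAP does not say whether that combined table uses the ongoing-period intensity. The table also groups events as administration site, systemic or any, so it cannot show which reaction became severe. The Grade 3-days table summarises days and does not give a percentage of participants.

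**Conclusion.** The gap follows from the text. A non-serious solicited event with onset in Days 1-4 that first reaches Grade 3 after Day 4 is Grade 3 in no event-level incidence table, while its ongoing days are counted as Grade 3 days. It is a reporting gap with a cheap remedy. It does not invalidate the 4-day rates and affects no hypothesis test.

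It may be tempting to conclude that the plan understates severe reactogenicity by a material amount. The documents do not support that: they give no rate for such events, and the count may be zero.

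The conclusion rests on two readings. The ongoing period is not defined; it is taken here as the days after Day 4, which fits an end date that may fall beyond the solicited period. That the data hold a maximum intensity for this period is inferred from SAP 6.2.3.9, where the rule is stated for a paper CRF. The trial uses a paper diary transcribed into an electronic CRF (Protocol 4.1 and 10.3.8), and the form itself is not among the documents.

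**What to change.** - Keep the Days 1-4 Grade 3 row as the main figure. SAP 6.2.2.4 needs no change.
- In SAP 4.3.2.1 and 6.2.2.3, add one row per solicited event: participants with onset in Days 1-4 and maximum intensity Grade 3 over the whole event, including the ongoing period as already used in 6.2.3.9.
- State that the combined 30-day Grade 3 table uses the same maximum intensity.
- Define the ongoing period, and confirm that the CRF holds its maximum intensity.
- As a programming check, require every participant with Grade 3 days for a solicited event to appear in that event's new row.

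**Cost.** SAP wording and 3 + 5 = 8 extra rows (three administration site and five systemic events). No new data are needed if the CRF holds what 6.2.3.9 relies on. The supplementary rate can only equal or exceed the Days 1-4 rate, so it may look slightly less favourable. It also mixes daily grades with a single ongoing-period maximum, which a footnote should say.
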